6.4 Study Intervention Compliance

Interruptions from the protocol-specified treatment plan require consultation between the investigator and the Sponsor and written documentation of the collaborative decision on participant management.

The date and (start and end) time of each dose administered in the clinic will be recorded in the source documents and recorded in the CRF. The dose of study intervention and study participant identification will be confirmed at the time of dosing by a member of the study-site staff other than the person administering the study intervention.

6.5 Concomitant Therapy

Medications or vaccinations specifically prohibited in the exclusion criteria are not allowed during time periods specified by this protocol. The investigator should discuss any questions regarding concomitant medication or vaccine with the Sponsor.

PROHIBITED MEDICATIONS

Listed below are specific restrictions for concomitant therapy during the course of the trial, from signing consent to the poststudy visit:

- Oral anticoagulants [Intradialytic heparin or other anticoagulants for injection (postdose only) are permitted]
- Antiplatelet medications (low dose aspirin is permitted)
- NSAIDs (e.g., ibuprofen) (acetaminophen used for minor ailments and topical NSAIDs is permitted)
- Other study interventions

RESTRICTED MEDICATIONS

Concomitant use of the following medications including FDCs will be allowed during the conduct of the study as long as the subject has been on a stable dose and treatment regimen for at least approximately 2 weeks prior and is able to withhold the use within four hours prior to administration of the dose of study intervention. This list is not exhaustive but serves as a guideline.

- Lipid Lowering Agents: Statins, Fibrates, Ezetimibe
- Anti-Hypertensive Medications: angiotensin converting enzyme (ACE) inhibitor, an angiotensin II receptor antagonist, beta blockers, calcium channel blockers, diuretic
- Diabetes Medications: Insulin, GLP-1 Analogs, Glinides, DPP-4 Inhibitors, α -GI
- Iron
- Phosphate Binders
- Vitamin D
- Erythropoietin
- HIF-PH inhibitors

6.5.1 Rescue Medications and Supportive Care

No rescue or supportive medications are specified for use in this study.

6.6 Dose Modification (Escalation/Titration/Other)

The dose of the study intervention to any participant may be adjusted downward based on newly available safety, PK and/or PD data observed in this study and/or other MK-2060 studies.

6.6.1 Stopping Rules

The following stopping rules will be used during the conduct of this study.

If any of the below stopping rules are met, the study will be paused, and no further dosing will occur until the Sponsor has reviewed the totality of data available. The study can be restarted based on joint agreement with the Sponsor and investigator. If needed, a substantial amendment may be submitted for approval.

1. An individual participant reports an SAE considered related to the study intervention by the investigator.
2. Two (2) or more participants (at the same dose level) report Severe Nonserious AEs considered related to the study intervention by the investigator.
3. If one or more infusion AEs of severe intensity considered related to the study intervention by the investigator occurs in 2 or more participants.
4. An increase aPTT > 4.0 -fold versus baseline as confirmed after repeat measurement in 2 or more participants. aPTT values from the central laboratory for safety will be used for this rule and aPTT measured at the Screening Visit should be used as baseline value.
5. An increase PT > 1.5 -fold versus baseline as confirmed after repeat measurement in 2 or more participants. PT values from the central laboratory for safety will be used for this rule and PT measured at the Screening Visit should be used as baseline value.

Participants who receive intradialytic heparin will likely have an increased aPTT at the 1-hour timepoint post dosing due to the pharmacologic effects of heparin. In order to allow for the evaluation of the pharmacologic effects of MK-2060 alone, the 12-hour post-dose aPTT will be the first timepoint used to assess aPTT stopping criteria for participants who receive intradialytic heparin. Heparin dosed at the time of dialysis should not interfere with aPTT at this 12-hour post-dose timepoint (heparin t_{1/2} is ~1hr). All other aPTT at safety labs throughout the course of the study will be drawn pre-dialysis and in the absence of heparin.

These criterion for aPTT (> 4.0 -fold in 2 or more participants) was based upon that aPTT prolongations greater than 3-fold have been observed in severe FXI-deficient populations [Asakai, R., et al 1991]. Using the same aPTT assay which was used by the central laboratory for PD in this study, samples of pooled normal human plasma were compared to those from FXI-deficient patients, which were tested individually [Ellsworth K 2018]. In normal human plasma, the clot time ranged between 31.8 and 36.4 seconds. In plasma from FXI deficient patients, the clot time ranged between 99.5 and 128.1 seconds, which corresponded to a range of 2.9 to 3.9-fold prolongation in aPTT compared to that of the normal human plasma. From data collected in MK-2060-001, it appears that higher doses of

MK-2060 provide similar inhibition as the severe FXI-deficient phenotype, evidenced by MK-2060-associated increases in aPTT (local lab) up to 3.9-fold at the highest dose in MK-2060-001 (120 mg administered subcutaneously). These aPTT prolongations occurred in the absence of prolongation of PT and were associated with >95% inhibition of FXI activity, with no evidence of MK-2060-related AE. Therefore, the stopping criterion based upon an aPTT is >4-fold after repeat measurement in 2 or more participants.

The safety of participants will be assessed on an ongoing basis, and while conditions that could warrant stopping dosing are not limited to those noted above, these criteria are meant to pre-specify circumstances under which the study may be stopped to review the available safety data. Importantly, if any criterion listed above occurs, further dosing will be stopped and review of available safety data by the investigator and Sponsor will be required prior to continuing the study, which might include modification of safety monitoring procedures.

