4.3.1 Rationale for Dose Interval and Study Design

This is a single dose study, in which participants will only receive one IV administration. MK-2060 or placebo will be given 30 minutes after the initiation of dialysis and administered via the post-dialyzer line (V side) over approximately 60 minutes. Participants will be enrolled and dosed on a rolling basis.

Dosing in this study will be initiated after at least **CC** days of safety data from the highest IV dose in MK-2060-013 (Single ascending dose study in Japanese healthy participants) has been reviewed.

MK-2060 is a fully human mAb and does not exhibit highly species-specific action, nor is it directed towards immune system targets. Safety assessment studies and clinical studies (MK-2060-001 and MK-2060-004) with MK-2060 provide no contraindications to the initiation of this study via IV routes. No dose-limiting toxicities were observed in the 4-week nonhuman primate toxicity trial. These considerations suggest that the risk of unanticipated severe reactions is low. However, due to uncertainties inherent in early phase clinical testing, this study will include a period of observation on a CRU after dosing. CRUs will have appropriate access to a full service acute-care hospital to facilitate rapid institution of medical intervention as indicated.

There will be frequent, careful assessments of AEs throughout the postdose period. The participants will be dosed and observed until discharge **CC** hours postdose; completion of dialysis on Day **CC** for safety monitoring, and then they will continue to be monitored throughout the study period as indicated in Section 1.3. Following discharge, the additional measures are being taken in this protocol to ensure the safety of study participants as indicated in Section 8.1.11.

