4.4.1 Clinical Criteria for Early Study Termination

There are no prespecified criteria for terminating the study early.

A primary objective of this early Phase 1 study is to identify the safe and well-tolerated dose and/or dosing regimen that achieve PK, pharmacodynamic, and/or biologic targets in humans based on preclinical or early clinical data. Therefore, it is possible that study participants may not receive all doses specified in the protocol if this objective is achieved at lesser dose levels in this study. This would not be defined as early termination of the study, but rather an earlier than anticipated achievement of the study objective(s). If a finding (eg, PK, pharmacodynamic, efficacy, biologic targets, etc) from another preclinical or clinical study using the study intervention(s), comparator(s), drug(s) of the same class, or methodology(ies) used in this study results in the study(ies) or program being stopped for nonsafety reasons, this also does not meet the definition of early study termination.

Early study termination is defined as a permanent discontinuation of the study due to unanticipated concerns of safety to the study participants arising from clinical or preclinical studies with the study intervention(s), comparator(s), drug(s) of the same class, or methodology(ies) used in this study.

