8.1.11 Domiciling

Participants will report to the CRU the day before the scheduled day of administration of the study intervention or the scheduled day of administration of the study intervention at the discretion of the investigator. Participants will remain in the CRU until the ~~CC~~-hour, postdose procedures (completion of dialysis on Day ~~CC~~ have been performed (Day ~~C~~ ~~CI~~). At the discretion of the investigator, participants may be requested to remain in the CRU longer.

Following discharge, the following measures are being taken in this protocol to ensure the safety of study participants:

- Participants will be informed that they could be taking an anticoagulant as a participant in this study, and that this might increase the risk of bleeding as might occur in surgery, dental procedures, or strenuous exercise/contact sport activities.
- Participants will be required to avoid scheduling any non-urgent/elective surgical or dental procedures, and to avoid strenuous physical activity and contact sport activities for the duration of the trial.
- Participants will be provided with an identification card, which identify them as participants in an anti-coagulant research study and, in the event of an emergency, will serve to notify healthcare providers that they might be at risk for provoked bleeding.
- If aPTT values are > 3-fold above baseline, or PT values are > 1.5-fold above baseline (at any time point), participants will be asked to remain in the clinic for at least ~~CC~~ hours, and until aPTT and/or PT values are no longer increasing (upon retest), at the discretion of the investigator. aPTT and PT values from the central laboratory for safety will be used and aPTT and PT measured at the Screening Visit should be used as baseline value.

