9.6 Statistical Methods

Safety

AEs will be tabulated by treatment. Summary statistics and plots will be generated for raw laboratory safety tests, ECGs, and vital sign as well as for change from baseline, as deemed clinically appropriate. Depending on the safety parameter, the difference from baseline will either be computed on the original scale (raw change from baseline) or on the log scale and back-transformed for reporting (percent change from baseline).

Pharmacokinetics

Values will be listed for each PK parameter and appropriate non-model based descriptive statistics will be provided: N (number of participants with non-missing data), arithmetic mean, standard deviation, arithmetic percent CV (calculated as 100 x standard

deviation/ arithmetic mean), median, minimum, maximum, geometric mean and geometric percent CV (calculated as $100 \times \sqrt{\exp(s^2) - 1}$, where s^2 is the observed variance on the natural log-scale).

Pharmacodynamics

Individual aPTT fold-change from baseline values will be natural log-transformed and evaluated with a linear mixed effect model containing fixed effects for treatment, time and treatment by time interaction and random effect for participant. Least squares means and 95% confidence intervals for each treatment, and for the between-treatment difference (MK-2060-placebo) and 90% CI at each dose level, will be obtained by time. These estimates will be back-transformed to obtain GM aPTT fold-change from baseline by treatment time and the GMR (MK-2060 fold-change from baseline/placebo fold-change from baseline) by dose and time.

The proportion of participants with a fold-increase in aPTT 168 hours after a single dose of at least **CC** will be tabulated.

Summary statistics will be provided for PD endpoints by time.

The relationship between plasma concentrations and aPTT, FXI activity, and PT may be explored graphically.

ADA

The number of participants with positive / negative antibody drug response to antibodies to MK-2060 will be summarized. Frequency counts for the maximum antibody titer for participants classified as positive will also be reported.

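### Only stopping rule 2 counts participants within a dose level; after a mid-study dose reduction, one severe related nonserious AE at each dose would not force a pause

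*Combined protocol and SAP*

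**What the plan says.** Section 6.6.1 pauses the study, with no further dosing until the Sponsor has reviewed the data, if any of five rules is met.

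- Rule 1 needs one participant with a related SAE.
- Rule 2: "Two (2) or more participants (at the same dose level) report Severe Nonserious AEs considered related to the study intervention by the investigator".
- Rule 3: "If one or more infusion AEs of severe intensity considered related to the study intervention by the investigator occurs in 2 or more participants".
- Rules 4 and 5 need a confirmed aPTT or PT increase in at least two participants, with no dose condition.

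The study plans one active dose, 50 mg, which is also the ceiling (Section 4.3). Section 6.6 says the dose "may be adjusted downward based on newly available safety, PK and/or PD data observed in this study" or in other MK-2060 studies. Section 4.3.1 adds: "Participants will be enrolled and dosed on a rolling basis".

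The protocol does not define a dose level. Section 9.6 plans a "between-treatment difference (MK-2060-placebo) and 90% CI at each dose level", and Section 4.4.1 allows for participants not receiving all doses "if this objective is achieved at lesser dose levels in this study". Table 2 in Section 6.1, on the other hand, lists the dosage level as 50 mg for the active arm and 0 mg for placebo.

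**The concern.** Rule 2 is the only automatic pause for severe related nonserious AEs other than infusion AEs and the two laboratory limits. That group includes nonserious bleeding. Section 8.1.11 has participants told that they could be on an anticoagulant and that "this might increase the risk of bleeding".

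The dose-level condition does nothing while everyone is assigned to the 50 mg plan. It starts to matter once the dose has been lowered, possibly because of safety data from this study. At that moment the rule 2 count starts again from zero, while the counts for rules 3 to 5 carry on. The protocol gives no reason for the difference. What is at stake is whether a second such event stops dosing automatically or only if someone decides that it should.

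There is also an ambiguity. Read literally against Table 2, whether two participants share a dose level depends on an assignment that the investigator and the involved Sponsor personnel do not know (Section 6.3.3).

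**Working it through.** **Logic check.** Take one severe, related, nonserious, non-infusion AE at 50 mg and one in another participant at a lower dose.

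- Rule 1: not met, because neither event is serious.
- Rule 2: not met, because the count is one at each dose level.
- Rule 3: not met, because neither is an infusion AE. Two severe related infusion AEs in the same pattern would meet it.
- Rules 4 and 5: not relevant, because they are laboratory limits.

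No mandatory pause follows.

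**Size.** The plan gives no operating characteristics for its stopping rules, so there is no stated figure to reproduce. Inputs:

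- Total of about 16 participants (Section 4.1).
- Assumed: a dose reduction after k = 8 participants, leaving 8 at the lower dose.
- Assumed: probability p per participant of a qualifying AE, independent and equal across arms and doses. The documents give no rate, so 1% to 20% is shown.
- Both arms count, because the rule is applied blind.

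Formulas:

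- Any two participants: 1 − P(Bin(16, p) ≤ 1).
- Within dose level: 1 − P(Bin(8, p) ≤ 1)².
- The two differ only when there is exactly one event at each dose, so the gap is [8p(1−p)^7]².

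| p | 8p(1−p)^7 | Any two participants | Within dose level | Gap (points) |
|---|---|---|---|---|
| 1% | 0.0746 | 1.1% | 0.5% | 0.6 |
| 2% | 0.1389 | 4.0% | 2.1% | 1.9 |
| 5% | 0.2793 | 18.9% | 11.1% | 7.8 |
| 10% | 0.3826 | 48.5% | 33.9% | 14.6 |
| 20% | 0.3355 | 85.9% | 74.7% | 11.3 |

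Gaps are computed before rounding.

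**Sensitivity.**

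- Reduction after 12 of 16: the gap is [12p(1−p)^11] × [4p(1−p)^3], which is 5.9, 11.0 and 8.4 points at 5%, 10% and 20%.
- Events only in active participants: the number on active is redacted. If it were 12, split 6 and 6, the gap would be 5.4, 12.5 and 15.5 points at the same three rates.
- No dose change: the gap is zero, provided a dose level means the planned dose with its placebo participants.

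**Why these are upper-end figures.** They count every qualifying AE as if it arose while dosing was still going on. AEs are collected for 164 days after a single dose, and an event after the last participant has been dosed changes nothing under either wording. The dosing period also looks short. The Synopsis gives about 8 months for the study (about 243 days) and up to 192 days per participant. That leaves 243 − 192 = 51 days, roughly 7 weeks, between first and last consent if participants use the full period.

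**The case against.** The strongest reply is that the gap lies outside the trial as planned. There is one active dose. The schema footnote and Section 4.3 tie a reduction to MK-2060-013 or other studies, and dosing starts only after safety review from MK-2060-013. A change made before the first dosing still leaves one dose level. Only Section 6.6 adds data from this study, and a reduction would then have to fall within a short dosing period. This stands, and it limits the size of the point. It does not remove it, because the protocol expressly permits that reduction.

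A second reply is that the backstops are good. Appendix 3 counts even a precautionary admission as serious, so many severe bleeds would meet rule 1 on the first event. Section 6.6.1 also says that "conditions that could warrant stopping dosing are not limited to those noted above". Both stand. Discretion is weaker than a mandatory pause, but it is not nothing.

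A third is that counting by dose is coherent, since lowering the dose is itself a mitigation. That is arguable, but the plan does not say so, and it does not do the same in rules 3 to 5.

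Two stronger readings are tempting. A reader might infer that rule 2 cannot be applied blind. Table 2 allows that reading, but Section 9.6 plans an active-minus-placebo contrast at each dose level, so the more natural meaning includes placebo participants and works blind. A reader might also start from exactly one AE already seen at 50 mg with 8 participants left, and quote a pause probability of 57% against 19% at a 10% rate. The first figure is 1 − 0.9^8; the second subtracts 8 × 0.1 × 0.9^7. The arithmetic is right, but it takes the rare scenario as given, at an unsupported rate, with every AE known before the next dosing. It does not describe the trial's risk.

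**Conclusion.** The point holds as a minor one. The dose-level condition in rule 2 is unexplained, ambiguous against Table 2, and opens a gap in the automatic pause only if the dose is lowered mid-study. If that happened after 8 of 16 participants, the chance of rule 2 ever being met would be lower by about 0.6 to 1.9 points at rates of 1% to 2%, and by 7.8 to 14.6 points at 5% to 20%. These figures rest on assumed rates, equal across arms and doses, on an assumed reduction, and on all events arising while dosing continues. If the dose stays at 50 mg the effect is zero on the natural reading. The documents do not support saying that participants are unprotected against repeated severe events, because rule 1, rule 3 and discretionary stopping all remain.

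**What to change.** Delete the five-word parenthesis from rule 2 so that it counts any two participants regardless of dose or arm, as rules 3 to 5 do. This also settles the Table 2 ambiguity and keeps the rule usable while blinded. If counting by dose is intended, define a dose level as the planned dose whatever the assignment, and state whether AEs seen at a higher dose carry over after a reduction.

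The cost is small. If the dose stays at 50 mg there are no extra pauses on the natural reading. After a reduction there may be a few more protective pauses, some from mixed-dose or active and placebo pairs. No hypothesis test is affected, because Section 9.8 states that none is prespecified.

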6.7 Intervention After the End of the Study

There is no study-specified intervention after the end of the study.

6.8 Clinical Supplies Disclosure

This study is blinded but supplies are provided as open label; therefore, an unblinded pharmacist or qualified study-site personnel will be used to blind supplies. Study intervention identity (name, strength, or potency) is included in the label text; random code/disclosure envelopes or lists are not provided.

The emergency unblinding call center will use the intervention randomization schedule for the study to unblind participants and to unmask study intervention identity. The emergency unblinding call center should only be used in cases of emergency (see Section 8.1.10). The Sponsor will not provide random code/disclosure envelopes or lists with the clinical supplies.

See Section 8.1.10 for a description of the method of unblinding a participant during the study, should such action be warranted.

6.9 Standard Policies

Not applicable.

7 DISCONTINUATION OF STUDY INTERVENTION AND PARTICIPANT WITHDRAWAL

7.1 Discontinuation of Study Intervention

In clinical studies with a single intervention, discontinuation of study intervention can only occur before the intervention. Therefore, participants who receive a single-dose intervention cannot discontinue study intervention.

7.2 Participant Withdrawal From the Study

A participant must be withdrawn from the study if the participant or participant's legally acceptable representative withdraws consent from the study.

If a participant withdraws from the study, they will no longer receive study intervention or be followed at scheduled protocol visits.

Specific details regarding procedures to be performed at the time of withdrawal from the study, as well as specific details regarding withdrawal from FBR, are outlined in Section 8.1.9. The procedures to be performed should a participant repeatedly fail to return for scheduled visits and/or if the study site is unable to contact the participant are outlined in Section 7.3.

7.3 Lost to Follow-up

If a participant fails to return to the clinic for a required study visit and/or if the site is unable to contact the participant, the following procedures are to be performed:

- The site must attempt to contact the participant and reschedule the missed visit. If the participant is contacted, the participant should be counseled on the importance of maintaining the protocol-specified visit schedule.
- The investigator or designee must make every effort to regain contact with the participant at each missed visit (eg, telephone calls and/or a certified letter to the participant's last known mailing address or locally equivalent methods). These contact attempts should be documented in the participant's medical record.

